  by analysisvariable;
  table trtvar/alpha=0.05 binomial (cl=blaker);
  ods output binomialcls=outputdsn2;
run;
```

Risk differences and 95% CI Using Miettinen-Nurminen:

```
proc freq data = analysis;tables trtvar*aval/ out=mncidat;run;

proc sort data=mncidat;by trtvar;run;

ods select PdiffCLs;
ods output PdiffCLs=mnci_d5v;
proc freq data=mncidat order=data;
  tables trtvar*aval /riskdiff (CL=( MN ));
  weight count;
run;
```

Odds ratios from logistic regression without MI:

```
proc logistic data=dataset out=imp_parms;
  class baseordscorevar (param=ref ref=5) basesteroidusevar (param=ref ref=no
steroid use) trtvar (param=ref ref=placebolabel);
  model aval (event='Yes') = trtvar baseordscorevar basesteroidusevar;
  oddsratio trtvar;
  ods output oddsratioswald = orest;
run;
```

Risk differences from logistic regression using the approach described in Ge et. Al [2]:

```
proc logistic data = dataset outmodel=pout;
  class trtvar ;
  model surv(event='1') = trtvar othercovariates ;
run;

*Create dataset tempa to contain all subjects and assign them the active treatment and
dataset tempg which include all subjects assigned the placebo treatment;

proc logistic inmodel=pout;
  score data = tempa out=preda(keep=id P_a rename= (P_1=P_a)) ;
run;

proc logistic inmodel=pout;
  score data = tempg out=predp(keep=id P_1 rename= (P_1=P_p)) ;
run;

proc sort data=pred1;by subjectid;run;
proc sort data=pred2;by subjectid;run;

*Combine to obtain risk differences in probabilities for each subject;

data comb;
  merge predp predp;
  by subjectid;
  diff=P_a-P_p;
run;

proc means data=comb;var diff;run;
```

To obtain the CI for the risk difference, use bootstrap with the following steps:

1. Sample with replacement from the dataset.
2. Obtain risk difference estimate for each bootstrap sample.
3. Repeat this step the above step 1000 times and use the 25th and 975th values from the sorted list of the 1000 risk estimates as the limits for the 95% CI for the risk difference. The risk difference estimate from bootstrap can be estimated as the mean of the 1000 risk estimates and should be equal to the risk difference obtained prior to performing bootstrap.

All statistical analyses and summaries will be performed on the mITT, ITT, and/or Safety populations. In general, the efficacy analysis will be performed mITT population and the safety analysis will be conducted on the Safety population. Any exceptions will be stated in the stage-specific appendix.

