6.4.2. Covariates for Secondary Endpoints

The main analysis for time to sustained recovery will use baseline steroid use and actual baseline ordinal score as covariates in a Cox regression model. P-value from the score test of this adjusted Cox model will be used to compare the covariate adjusted time to sustained recovery between treatment arms. This analysis will be referred to as the primary analysis of the time to sustained recovery endpoint. In the supplemental analysis, time to sustained recovery endpoint will be analyzed using baseline steroid use, actual baseline ordinal score, continuous age, and continuous duration of symptoms prior to enrollment as covariates in the Cox model.

Survival without respiratory failure up to and including Study Day 29 will be analyzed only for subjects with an actual baseline ordinal score of 5 or 6. The main analysis for this endpoint will use a logistic regression model adjusted for baseline ordinal score (5 vs 6/7), baseline dexamethasone use (yes or no), continuous

baseline CRP value, and continuous age as covariates. Additionally, the proportion of subjects who are alive and without respiratory failure up to and including Study Day 29 will be presented by treatment along with 95% and 80% CI estimated from Kaplan Meier. As a sensitivity analysis, survival without respiratory failure will be analyzed using a logistic regression model adjusting for baseline steroid use and actual baseline ordinal score as covariates. A supplemental analysis of this endpoint will use a logistic regression model adjusting for baseline steroid use, actual baseline ordinal, continuous age, and continuous duration of symptoms prior to enrollment.

The analysis of the time to mechanical ventilation or death will include baseline ordinal score (5 vs 6/7), baseline dexamethasone use (yes or no), baseline CRP value and age as covariates in the Cox regression model.

A detailed list of covariates and subgroup analyses to be performed for secondary endpoints is also provided in [Table 6](#).

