	Primary with Sensitivity Imputation 1	
 Use the complete data for ordinal score to derive sustained recovery. Subjects whose last assessment in the study is prior to Day 57 (beginning of Day 60 window) after discharge from the hospital to a location other than LTAC, hospice care or other hospital will be treated as recovered by Day 60. Their time to recovery will be the day of their first observed/imputed recovery score (i.e., 1, 2, 3) or the day of discharge, whichever comes first. Subjects whose last assessment in the study is prior to Day 57 (beginning of Day 60 window) without being discharged from the hospital to a location other than LTAC, Hospice care or other hospital at their last assessment will be considered not recovered and censored at the date of their last assessment.

Endpoint	Analysis	Imputation Method
		
 Death prior to recovery will be considered not recovered and censored at expected study Day 60.
	Supplementary	
 Same imputation method as primary analysis for time to sustained recovery.
	Subgroup	
 Repeat analysis for each subgroup using same imputation as primary analysis for this endpoint.
2. Survival without respiratory failure up to and including Study Day 29	Primary	
 Subjects who complete follow-up without mechanical ventilation or death or who have the event after Day 29 will be considered non-events and censored at Day 29. Subjects whose last assessment in the study is before Day 26 (beginning of Day 29 window) and before experiencing death or progression to mechanical ventilation will be considered non-events and censored at the last assessment. Subjects whose last assessment in the study is before Day 29 but within window for Day 29 (i.e., Day 26, 27, 28) and before experiencing death or progression to mechanical ventilation will be considered non-events regardless of their discharge status and censored at Day 29.

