	Primary with Sensitivity Imputation	
 Subjects who complete follow-up without mechanical ventilation or death or who have the event after Day 29 will be considered non-events and censored at Day 29. Subjects whose last assessment in the study is before Day 26 (beginning of Day 29 window) and before experiencing death or progression to mechanical ventilation and were discharged to a location other than LTAC, hospice care, or other hospital will be considered non-events and censored at Day 29. Subjects whose last assessment in the study is before Day 26 (beginning of Day 29 window) and before experiencing death or progression to mechanical ventilation without being discharged to a location other than LTAC, hospice care, or other hospital will be considered non-events and censored at the last assessment. Subjects whose last assessment in the study is before Day 29 but within window for Day 29 (i.e., Day 26, 27, 28) and before experiencing death or progression to mechanical ventilation will be considered non-events regardless of their discharge status and censored at Day 29.
	Sensitivity	
 Same imputation method as primary analysis of this endpoint
	Supplementary	
 Same imputation method as primary analysis of this endpoint
	Subgroup	
 Repeat analysis for each subgroup using same imputation as primary analysis for this endpoint
	Other Secondary Endpoints: Efficacy	
1. Time to 1-point improvement by Day 60	Primary	
 Use the complete data for ordinal score to define time to improvement. Subjects whose last assessment in the study is prior to an observed improvement will be censored at the day of their last assessment. Subjects who complete follow-up but do not experience improvement will be censored at the day of their Study Day 60. Death prior to improvement will be considered not improved and censored at expected study Day 60.
	Subgroup	
 Repeat analysis for each subgroup using same imputation as primary analysis for this endpoint.

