Each subgroup from [Table 6](#) will be considered separately, and the tabular and graphical summaries described above will be replicated for each subgroup ([Table 20](#)). A forest plot will be generated to display 95% and 80% CIs for hazard ratios from each of the subgroup analyses ([Figure 16](#), [Figure 17](#)).

Proportion of Subjects Alive and Without Respiratory Failure up to and Including Study Day 29

Any subjects whose last assessment is prior to death or progression to respiratory failure and prior to Day 26 (beginning of Day 29 window) will be censored at the date of their last observed assessment. For the sensitivity analysis of this endpoint, subjects whose last assessment is prior to obtaining the event and who were discharged to a location other than LTAC, hospice care, or other hospital will be considered recovered and censored at Day 29. For both primary and sensitivity analysis of this endpoint, subjects who complete follow-up will be censored Day 29. Events that occur after Day 29 will be censored at Day 29.

Kaplan-Meier estimates for the proportion of subjects with baseline ordinal score 5 or 6, who are alive and without respiratory failure up to and including Study Day 29 will be presented by treatment along with 95% CI from Kaplan-Meier (Table 30). Odds ratios and a p-value from an adjusted logistic regression model adjusting for covariates [2] detailed in Table 6 will be presented in Table 30. Risk differences and corresponding CIs obtained through bootstrap will also be generated using the approach discussed in [2] and results will be reported in Table 30. This analysis will be referred to as the primary analysis for the survival without respiratory failure endpoint.

Refer to Table 6 for a list of covariates and subgroup analyses for this endpoint. Refer to Table 7 for imputation methods to be applied to this endpoint.

Results of the primary, sensitivity, and subgroup analyses for this endpoint are reported in Table 30.

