	Treatment A (N=X)	6	x	x	x.x	x.x, x.x	x.x, x.x	x.xx	x.xx, x.xx	x.xx, x.xx
	Treatment B (N=X)		x	x	x.x	x.x, x.x	x.x, x.x			
	Treatment A (N=X)	7	x	x	x.x	x.x, x.x	x.x, x.x	x.xx	x.xx, x.xx	x.xx, x.xx
	Treatment B (N=X)		x	x	x.x	x.x, x.x	x.x, x.x			
	Treatment A (N=X)	Any BOS	x	x	x.x	x.x, x.x	x.x, x.x	x.xx	x.xx, x.xx	x.xx, x.xx
	Treatment B (N=X)		x	x	x.x	x.x, x.x	x.x, x.x			

N = Number of subjects in the specified treatment group, actual baseline ordinal score, and analysis population.

n = Number of recovered subjects.

Difference is the difference in the restricted mean recovery time between active treatment to placebo.

^a Tau is the truncation time point for the Restricted Mean Survival Time analysis and is equal to the minimum of the largest observed times in each group.

Programming

Within an actual baseline ordinal score stratum:

```
proc lifetest data=enrevent plots=(rmst) method=breslow rmst(cl);
by stratum;
time evntday * Censor(1);
strata trtcode /diff=all;
ods output rmst=rmst;
run;
```

Table 30: Proportion of Subjects Alive and Without Respiratory Failure through Day 29 — mITT Population

Analysis/Subgroup	Category	Treatment A (N=x)		Treatment B (N=x)		Odds Ratio			Risk Difference ^g			P-value ^h
		n	% (95%CI) ^f	n	% (95%CI) ^f	Estimate	95% CI	80% CI	Estimate	95% CI	80% CI	
Initial model, Age, Baseline OS, Dexamethasone Use, and CRP ^a	-	x	x.x (x.x, x.x)	X	x.x (x.x, x.x)	x.x	x.x, x.x	x.x, x.x	x.x	x.x, x.x	x.x, x.x	0.xxx
Primary with Sensitivity Imputation 1 ^b	-	x	x.x (x.x, x.x)	X	x.x (x.x, x.x)	x.x	x.x, x.x	x.x, x.x	x.x	x.x, x.x	x.x, x.x	0.xxx
Sensitivity Analysis 1: Baseline OS and Steroid Use ^c	-	x	x.x (x.x, x.x)	x	x.x (x.x, x.x)	x.x	x.x, x.x	x.x, x.x	x.x	x.x, x.x	x.x, x.x	0.xxx
Supplemental Analysis 1: Impact of age and duration of symptoms prior to enrollment ^d	-	x	x.x (x.x, x.x)	x	x.x (x.x, x.x)	x.x	x.x, x.x	x.x, x.x	x.x	x.x, x.x	x.x, x.x	0.xxx
Subgroup Analyses^e												
Baseline Ordinal Score	5	x	x.x (x.x, x.x)	x	x.x (x.x, x.x)	x.x	x.x, x.x	x.x, x.x	x.x	x.x, x.x	x.x, x.x	0.xxx
	6 or 7	x	x.x (x.x, x.x)	x	x.x (x.x, x.x)	x.x	x.x, x.x	x.x, x.x	x.x	x.x, x.x	x.x, x.x	0.xxx
Repeat for all subgroups from Table 6		x	x.x (x.x, x.x)	x	x.x (x.x, x.x)	x.x	x.x, x.x	x.x, x.x	x.x	x.x, x.x	x.x, x.x	0.xxx

CI=Confidence Internals. OR=Odds Ratios. NA=Not applicable.

N=Number of subjects in the modified-intent-to-treat (mITT) population. n=Number of subjects without respiratory failure or death through Day 29.

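### For survival without respiratory failure through Day 29, the planned sensitivity imputation cannot change the logistic odds ratio, risk difference or p-value

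*SAP*

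**What the plan says.** The endpoint is survival without respiratory failure up to and including Day 29, in subjects with baseline ordinal score 5 or 6.

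- **Model.** SAP Section 6.4.2: "The main analysis for this endpoint will use a logistic regression model", adjusted for baseline score, dexamethasone use, CRP and age. Section 8.2.1 takes the Table 30 odds ratio and p-value from that model, and the risk difference from its predictions with bootstrap limits. The percentages are Kaplan-Meier estimates.
- **Primary rule (Table 7).** Event-free subjects last assessed before Day 26 "and before experiencing death or progression to mechanical ventilation will be considered non-events and censored at the last assessment".
- **Sensitivity imputation (Table 7).** Such subjects who had a good discharge "and were discharged to a location other than LTAC, hospice care, or other hospital will be considered non-events and censored at Day 29". Those "without being discharged to a location other than LTAC, hospice care, or other hospital will be considered non-events and censored at the last assessment".
- **Other rows for this endpoint.** The sensitivity and supplementary analyses use the "Same imputation method as primary analysis of this endpoint", and the subgroup analyses do likewise.
- **Section 8.2.1.** Subjects last assessed "prior to death or progression to respiratory failure and prior to Day 26 (beginning of Day 29 window) will be censored" at their last assessment; it does not say that they count as non-events.
- **Table 30.** The count column is defined as "n=Number of subjects without respiratory failure or death through Day 29". Note a (primary) calls early losses non-events. Note b (sensitivity) says so only for good discharges and calls the rest censored. Note f, attached to the percentage columns, censors everyone event-free and last seen before Day 29 at the last assessment.

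**The concern.** A sensitivity imputation is useful only if it changes something the analysis uses. Here the two rules appear to differ only in a censoring date, and a logistic regression does not read one. If so, the sensitivity row would reproduce the primary odds ratio, p-value and risk difference whatever the data, and a reader could take that agreement as evidence of robustness.

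The assumption most open to question is that a subject lost while still in hospital, or after discharge to hospice, LTAC or another hospital, survived to Day 29 without ventilation. It would then go untested in every logistic analysis of a key secondary endpoint. For the Day 8 primary endpoint, by contrast, Table 7 does vary the handling of such subjects: multiple imputation in the primary analysis, last observation carried forward in Sensitivity Imputation 2.

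**Working it through.** **1. The two rules side by side (Table 7)**

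| Event-free subject | Primary: status, time | Sensitivity: status, time |
|---|---|---|
| Completes follow-up, or event after Day 29 | non-event, Day 29 | non-event, Day 29 |
| Last seen Day 26–28 | non-event, Day 29 | non-event, Day 29 |
| Last seen before Day 26, good discharge | non-event, last assessment | non-event, Day 29 |
| Last seen before Day 26, no good discharge | non-event, last assessment | non-event, last assessment |

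The status column is the same throughout. One cell of the time column changes.

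**2. What the model reads.** The logistic pseudocode in Section 6.1 is "model aval (event='Yes') = trtvar baseordscorevar basesteroidusevar". The covariates differ for this endpoint, but the form is the same: a binary outcome and no time or censoring variable. The risk-difference code in that section averages predictions from the same kind of model. Identical status and covariates give identical estimates. Only the bootstrap limits of the risk difference could differ, through resampling noise.

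**3. Numerical check.** The plan gives no figure to reproduce. Both rules were coded and run on 500 simulated trials. Assumptions not taken from the documents: 200 subjects with baseline score 5 or 6, about 15% lost, 60% of losses with a good discharge. The logistic model used treatment, baseline score, dexamethasone, CRP and age.

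- Largest difference between rows in odds ratio, risk difference and p-value: 0.
- Largest difference in a Kaplan-Meier percentage: 4.5 points in an arm.
- One example trial (27 early losses, 13 with a good discharge): OR 1.458, risk difference 0.0632, p = 0.282 in both rows. Kaplan-Meier success (control/active) was 70.8%/73.6% in the primary row and 71.5%/75.3% in the sensitivity row.

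**4. How much the untested assumption could matter.** The documents give neither loss rates nor the number per arm with baseline score 5 or 6. Assume true success of 75% in both arms (true OR 1.00), and let *loss* be the proportion lost without a good discharge and *risk* their true event probability.

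- Present rule: observed success = 0.75 + loss × risk.
- Losses coded as failures: observed success = 0.75 − loss × (1 − risk).

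| Loss, arm 1 vs arm 2 | Risk | Present rule: success, OR (arms reversed) | Failure coding: success, OR (arms reversed) |
|---|---|---|---|
| 2% vs 1% | 25% | 0.755 vs 0.7525, 1.01 (0.99) | 0.735 vs 0.7425, 0.96 (1.04) |
| 2% vs 1% | 50% | 0.760 vs 0.755, 1.03 (0.97) | 0.740 vs 0.745, 0.97 (1.03) |
| 10% vs 5% | 25% | 0.775 vs 0.7625, 1.07 (0.93) | 0.675 vs 0.7125, 0.84 (1.19) |
| 10% vs 5% | 50% | 0.800 vs 0.775, 1.16 (0.86) | 0.700 vs 0.725, 0.89 (1.13) |

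For 10% vs 5% at 25% risk under the present rule, ln(1.073) is about 0.21 standard errors at 100 per arm and 0.19 at 80.

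Equal loss of 5% in both arms gives OR 1.00 only because the true OR is 1. With true success of 85% vs 75%, 50% risk and 5% loss in each arm, observed success is 0.875 vs 0.775: OR 2.03 against a true 1.89.

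**The case against.** *A companion analysis covers this.* Time to ventilation or death through Day 29 (Section 8.2.2, Tables 42 and 43) concerns the same events with the same covariates, and has its own sensitivity imputation. It is a Cox analysis, so the changed censoring date can move the hazard ratio and p-value. The Table 42 shell, whose format Table 43 shares, also has a row for baseline score 5 or 6. This stands, and it limits the harm. But it yields a hazard ratio for a separately listed secondary endpoint and does not test the key secondary odds ratio or p-value.

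*The row is partly functional.* Under Table 7 and note b the Kaplan-Meier percentages do respond, and Section 15.3 describes this sensitivity analysis in terms of censoring. That also stands. However, note f read literally would freeze the percentages too, and it contradicts note b and the Day 26–28 rule.

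*Censored subjects might be dropped from the logistic model.* Section 8.2.1 and note b allow that reading. In the example trial, dropping them gives OR 1.447 (p = 0.317) in the primary row and 1.508 (p = 0.251) in the sensitivity row. But Table 7 and note a call these subjects non-events, and no rule in the SAP drops them.

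*Few subjects are affected.* Section 6.5.1 provides for chart review and optional blinded adjudication before Table 7 is applied, which should leave few unresolved losses. This is a fair point about the size of any bias. It does not make the check work.

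*Worst-case coding is a choice, not a requirement.* True, and the table above shows it can lie further from the truth than the present rule. It is therefore proposed only for the sensitivity row.

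**Conclusion.** The concern holds. Under Table 7 as written, the sensitivity imputation changes the logistic odds ratio, p-value and risk-difference estimate by zero, by construction, at any loss rate. The count column cannot change either. Only the Kaplan-Meier percentages can move, provided note f is not taken literally. This rests on keeping the censored subjects in the logistic model as non-events, which is what Table 7 and note a say.

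The bias in the primary result is probably small. The illustrative odds ratios of 1.01 to 1.16 (0.86 to 0.99 with the arms reversed), against a true 1.00, depend entirely on the assumed loss and risk. The defect is a planned missing-data check on a key secondary endpoint that cannot respond in the columns carrying the treatment comparison. It should be corrected. The Day 8 primary endpoint is not affected.

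**What to change.** 1. Leave the primary rule for this endpoint unchanged.
2. In the Table 7 sensitivity row and Table 30 note b, keep good discharges as non-events. For the logistic model, code as respiratory failure or death those event-free subjects lost before Day 26 without a good discharge who remain unresolved after chart review and any adjudication.
3. Label this an alternative missing-data assumption, worst case within each arm. It is not a conservative bound on the treatment effect, since it can move the odds ratio either way.
4. State in notes a and b the 0/1 value each group takes in the logistic model, and use the word *censored* only for the Kaplan-Meier estimate.
5. Reconcile Section 8.2.1 and notes a, b and f with Table 7's Day 26 rule and with the sensitivity row.

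The cost is one re-run of the existing model and its bootstrap with a changed outcome code, plus wording edits. It needs no new data and does not touch the primary result. Section 6.5.1 lets a stage-specific SAP set different missing-data rules. None is among the documents; if one exists for this stage, it should be checked for the same point.
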